8.8 Length of Hospital Stay

The length of the hospital and intensive care stay (if applicable) will be captured.

9 ADVERSE EVENTS

9.1 Definitions

Adverse Event

For this study, an adverse event is defined as any undesirable clinical occurrence in a patient that may be attributable to the study procedure or device.

Serious Adverse Event (SAE)

A serious adverse event (SAE) is an adverse event that results in one or more of the following for this study:

- Death;
- Life-threatening: life-threatening means that the subject was at immediate risk of death from the reaction as it occurred;
- Requires inpatient hospitalization or prolongation of existing hospitalization;
- Results in persistent or significant disability/incapacity. Disability is defined as a substantial disruption of a persons' ability to conduct normal life functions;
- Is a congenital anomaly or birth defect; or
- Is an important medical event, based upon appropriate medical judgment, and may jeopardize the subject or may require medical or surgical intervention to prevent one of the outcomes listed above (e.g. death, life-threatening, hospitalization, etc.).

Unanticipated Adverse Device Effect (UADE)

Unanticipated adverse device effect (UADE) is any serious adverse effect on health or safety, any life-threatening problem or death caused by, or associated with a device, if that effect, problem, or death was not previously identified in nature, severity, or degree of incidence in the investigational plan or IDE application (including a supplementary plan or application), or any other unanticipated serious problem associated with a device that relates to the rights, safety, or welfare of subjects.

Associated with the investigational device: There is a reasonable possibility that the adverse effect may have been caused by the investigational device.

Life-threatening adverse effect: Any adverse effect that places the subject, in the view of either the investigator or the sponsor, at immediate risk of death from the effect **as it occurred**. It does not include a reaction that, had it occurred in a more severe form, might have caused death.

Serious adverse effect: An adverse effect is considered “serious” if, in the view of either the investigator or the sponsor, it results in any of outcomes described in the definition of SAE (see definition of SAE above).

Unanticipated adverse effect: Any adverse effect, the nature, specificity, severity, or frequency of which is not consistent with the risk information in the clinical study protocol or elsewhere in the current IDE application.

9.2 Collection of Adverse Events and Adverse Effect Information

All adverse events and adverse effects, serious and non-serious, will be collected from the time a subject signs the informed consent through the last study visit. Clinical study subjects will be routinely questioned about adverse effects at study visits.

9.3 Management of Adverse Events

The Investigator will manage each adverse event/adverse effects in accordance with accepted standards of medical care, with primary attention to the well-being of the subject. To the extent appropriately possible, achievement of study objectives will be considered. The investigator will arrange for provision of care by other professionals (e.g., emergency service providers, hospital, and consulting specialist) as needed.

9.4 Recording and Assessment of Adverse Effects

All observed or volunteered adverse effects (serious or non-serious) and abnormal test findings, regardless of treatment group, if applicable, or suspected causal relationship to the investigational device or, if applicable, other study treatment or diagnostic product(s) will be recorded in the subjects’ case histories (eCRF). For all adverse effects, sufficient information will be pursued and/or obtained so as to permit 1) an adequate determination of the outcome of the effect (i.e., whether the effect should be classified as a *serious adverse effect*) and; 2) an assessment of the casual relationship between the adverse effect and the investigational device or, if applicable, the other study treatment or diagnostic product(s).

Adverse effects or abnormal test findings felt to be associated with the investigational device or, if applicable, other study treatment or diagnostic product(s) will be followed until the effect (or its sequelae) or the abnormal test finding resolves or stabilizes at a level acceptable to the sponsor-investigator.

9.5 Abnormal Test Findings

An abnormal test finding will be classified as an *adverse effect* if one or more of the following criteria are met:

- The test finding is accompanied by clinical symptoms;

- The test finding necessitates additional diagnostic evaluation(s) or medical/surgical intervention; including significant additional concomitant drug or other therapy (Note: simply repeating a test finding, in the absence of any of the other listed criteria, does not constitute an adverse effect.);
- The test finding leads to a change in study treatment or exposure or discontinuation of subject participation in the clinical study; or
- The test finding is considered an adverse effect by the sponsor-investigator.

9.6 Adverse Event Severity

The investigator is responsible for assessing the severity of an adverse event. A change in severity may constitute a new reportable adverse event. The following guideline should be used to determine the severity of each adverse event:

- Mild: Awareness of signs or symptoms, but does not interfere with the patient's usual activity, or is a transient event that resolves without treatment and with no sequelae.
- Moderate: Discomfort enough to cause a noticeable impact on the subject's daily life.
- Severe: Incapacitation or significant impact on the subject's daily life.

9.7 Adverse Event Causality

It is the Investigator's responsibility to assess the relationship between all adverse events and the study procedure. Only adverse events attributable (relationship of possibly, related, or unknown) to a device or the study procedure are to be recorded in the eCRF.

- Possibly: A clinical event (including abnormal laboratory result) that presents an unlikely association between device/procedure, which cannot be ruled out with certainty, but could also be explained by alternative etiology.
- Related: A clinical event (including abnormal laboratory result) that presents a strong temporal relationship between device/procedure, in which an alternative etiology is unlikely.
- Unknown: A clinical event (including abnormal laboratory result) that cannot be determined to be related or unrelated to device/procedure given the information obtained.

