9.8 Reporting Adverse Events

The Investigator is required to report all adverse events experienced by the patient from the day of the surgical procedure (Visit 2) until the patient completes Visit 3 (30 days after the surgical procedure) or withdraws early (prior to Visit 3). All adverse events (both serious and non-serious), regardless of their relatedness to the study device or procedure, must be reported in the Adverse Event eCRF. The investigator will evaluate the severity of the event, and its relatedness to the study device or procedure. Both severity and relatedness of all adverse events need to be entered in the Adverse Event eCRF.

Any necessary medical management of the event will be recorded in the patient's medical record/source document. All adverse events must be followed until resolution or until they become stable but ongoing.

The Investigator will record all adverse events (both serious and non-serious) in the source documents. Standard medical terminology should be used when recording adverse events. In addition, the following information should be recorded:

- Onset date
- Resolution date or date of death
- Severity of the event
- Action taken
- Event status (ongoing at study end or resolved)
- Relationship of adverse event to the device used in the study
- Relationship of the adverse event to the study surgical procedure
- Indication of whether the event is serious.

Data related to SAEs will be collected until event resolution, or until the event is considered stable, or until all attempts to determine the resolution of the event are exhausted. All adverse events that are unresolved at study completion (or early termination) will be recorded as ongoing at study end.

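### Sections 9.7 and 9.8 give opposite rules for entering unrelated adverse events in the eCRF, and the causality scale has no 'not related' level

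*Combined protocol and SAP*

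**What the plan says.** Section 9.7 (Adverse Event Causality) limits what sites enter: "Only adverse events attributable (relationship of possibly, related, or unknown) to a device or the study procedure are to be recorded in the eCRF". It then defines three levels. *Possibly* covers an association thought improbable, "which cannot be ruled out with certainty, but could also be explained by alternative etiology". *Related* covers a strong temporal link where another cause is unlikely. *Unknown* covers an event that "cannot be determined to be related or unrelated to device/procedure given the information obtained".

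Section 9.8 (Reporting Adverse Events) says that all events, serious and non-serious, "regardless of their relatedness to the study device or procedure, must be reported in the Adverse Event eCRF". It adds: "Both severity and relatedness of all adverse events need to be entered in the Adverse Event eCRF". The same section requires all events in the source documents and lists two separate items to record: "Relationship of adverse event to the device used in the study" and "Relationship of the adverse event to the study surgical procedure".

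Section 11.2.6 (Safety Analyses) plans a causality summary with the same three levels as section 9.7.

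**The concern.** Both sections are current protocol text and both govern the same form. For an event judged unrelated, one forbids the entry and the other requires it. With 10 to 15 sites planned, practice could differ between sites, and the counts by system organ class and preferred term would then depend partly on which section each site followed.

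Section 4.1 describes the trial as open-label. Under section 9.7, attribution by an investigator who knows the arm becomes a condition for a non-serious event to enter the database at all. That judgment could differ by arm, although nothing in the documents shows that it would. Under section 9.8 the event is entered, but no level defined in the protocol describes it. Safety is half of the study objective, and the trial is meant to support a PMA application, so the content of the safety tables should not depend on which paragraph a site happened to read.

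**Working it through.** No figure in the plan bears on this point and no formula applies. The check sets the sections side by side and then tests the scale.

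**Step 1. What each section implies for an event judged unrelated to device and procedure**

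| Section | Rule | Unrelated event |
|---|---|---|
| 9.1 | Possible attribution is part of the adverse event definition | Leans towards leaving it out |
| 9.2 | Collection of all events, silent on relatedness | Neutral |
| 9.4 | Adverse effects and abnormal findings go in the eCRF "regardless of treatment group, if applicable, or suspected causal relationship to the investigational device" | Enter |
| 9.7 | eCRF restricted to possibly, related, unknown | Do not enter |
| 9.8 | All events in the Adverse Event eCRF, each with relatedness | Enter |
| 9.8.1 | SAEs reported whatever the cause; SAE form should agree with the eCRF | SAE reported; an eCRF record is needed for the comparison |
| 11.2.6 | Causality summary with three levels | No row |

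Sections 9.7 and 9.8 are incompatible. Sections 9.4 and 9.8.1 support 9.8.

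**Step 2. Does the definition in section 9.1 resolve the conflict?** If it already removed unrelated events, the phrases in 9.8 and 9.8.1 that extend reporting to all events whatever their relatedness would have little to act on, and the restriction in 9.7 would be largely redundant. The definition is therefore a third text to reconcile.

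**Step 3. Test the three levels against an event the investigator has judged unrelated.**
- *Related*: excluded by the judgment itself.
- *Possibly*: requires that an association cannot be excluded. The investigator has excluded it.
- *Unknown*: requires that relatedness cannot be determined. The investigator has determined it.

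Count: 3 levels defined in 9.7, the same 3 tabulated in 11.2.6, and 0 of them 'not related'. On the protocol's own scale, an unrelated event entered under 9.8 is either left unrated or placed in a level that does not fit.

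**Step 4. Device and procedure.** Section 9.8 lists 2 relationship items. An event clearly due to surgery but not to the device passes the filter in 9.7, because that filter accepts attribution to either. It still has no fitting value for the device item. The missing level therefore matters even for some events that 9.7 admits.

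**Step 5. Which events are exposed.** Under 9.7 the loss is confined mainly to non-serious events judged unrelated to both device and procedure. SAEs are still reported under 9.8.1. An unrelated SAE would, however, have a report form and no eCRF record to compare it with.

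**The case against.** The strongest reply has four parts.

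- **The scale is complete on its own terms.** Read alone, section 9.7 names the levels that qualify an event for entry and so implies an excluded remainder. The missing level is then largely a by-product of the recording conflict, and the eCRF may already offer it. *This stands in part.* The eCRF is not among the documents, so its field is unknown. The protocol still defines no such level, and 9.4 and 9.8 require entry.
- **The two relationship items may describe source documents.** The list in 9.8 follows a sentence about source recording, and 9.7 rates device and procedure jointly. *The reading is fair but does not remove the need.* Wherever the two items are recorded, an event due only to surgery needs a 'not related' value for the device.
- **The loss is detectable and limited.** Events should be in source documents, section 10.2 provides for checking eCRF entries against source, and section 14.10 sends missing data back to sites. The tables by system organ class and preferred term have no causality filter, so events entered under 9.8 are counted there. *All of this stands and lowers the risk of permanent loss.* None of it tells a monitor which rule governs, so an omission under 9.7 need not be treated as an error.
- **The consequences are thin.** Safety is descriptive, a difference by arm is not shown, and few events may be lost. *This stands* and limits how serious the point is.

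**Conclusion.** The concern holds. Sections 9.7 and 9.8 give contradictory instructions for the same form, and the protocol defines no causality level for an event judged unrelated. The effect on the safety tables cannot be sized: the documents give neither an adverse event rate nor the share of events judged unrelated. It is probably modest, because SAEs are reported regardless of cause and 9.7 retains even improbable associations with the device or the surgery. Bias between arms is possible in an open-label trial but not demonstrated. Efficacy results, sample size and error rates are untouched.

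The conclusion rests on the protocol text alone and assumes nothing about how the eCRF is built. The text should be corrected. The later SAP announced in section 11 could add a row to the causality table, but it cannot settle which events sites enter.

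**What to change.** Make one recording rule and one complete scale:

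1. Delete the sentence in section 9.7 that restricts eCRF entry to attributable events.
2. Define an adverse event in section 9.1 without reference to attribution.
3. Keep the rule in section 9.8 that all adverse events are entered in the eCRF with a relatedness rating.
4. Add 'not related' to the scale in section 9.7 and to the causality summary in section 11.2.6. Check that the eCRF relatedness field offers it, and add it if not.

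The cost is protocol wording in three sections, one eCRF check and slightly more data entry. If subjects have already been treated, sites that followed 9.7 need a source check for omitted events.

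A separate mismatch is not settled by this change: section 9.2 starts collection at consent, while section 9.8 starts it on the day of surgery. It should be reconciled in the same amendment.

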11.2.6 Safety Analyses

Safety analysis will be performed on the safety population using descriptive statistics without inferential tests for significance. Safety evaluation will include monitoring of adverse events (adverse events/SAEs). Adverse events will be coded using the current version of the Medical Dictionary for Regulatory Activities (MedDRA). Treatment-emergent adverse events will be presented in summary tables by system organ class (SOC), preferred term and by treatment group. The number and percentage of subjects within each SOC and preferred term and the number of adverse events within each SOC and preferred term will be presented. The summary of adverse events by severity (mild, moderate, or severe) will be tabulated. The summary of adverse events by causality (possibly related, related, unknown) will also be provided. For each patient and each adverse event, the worst severity and causality recorded will be used in the by-intensity and by-relationship summaries.

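### The causality scale defines 'Possibly' as an unlikely association, so unlikely events are tabulated as possibly related, while plausible device effects with a competing cause can only default to 'Unknown'

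*Combined protocol and SAP*

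**What the plan says.** Section 9.7 gives the investigator three causality levels.

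- *Possibly*: an event that "presents an unlikely association between device/procedure, which cannot be ruled out with certainty, but could also be explained by alternative etiology".
- *Related*: an event that "presents a strong temporal relationship between device/procedure, in which an alternative etiology is unlikely".
- *Unknown*: an event that "cannot be determined to be related or unrelated to device/procedure given the information obtained".

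There is no level called unlikely and none called not related. All three levels count as attributable for recording: "Only adverse events attributable (relationship of possibly, related, or unknown) to a device or the study procedure are to be recorded in the eCRF".

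Section 11.2.6 carries the same three levels into the safety tables: "The summary of adverse events by causality (possibly related, related, unknown) will also be provided". The level defined by an unlikely association thus appears there under the label possibly related.

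Section 9.1, within the definitions for unanticipated adverse device effects, sets a different test for an effect associated with the device: "There is a reasonable possibility that the adverse effect may have been caused by the investigational device".

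**The concern.** The label and the definition of *Possibly* point in different directions. To a reader of a safety table, possibly related means that a device cause is a real candidate. The definition says that the association is unlikely. An investigator who follows the definition puts weakly linked events in that row. The same investigator has no natural place for an event with a realistic device link and a realistic other cause, a common situation after open surgery.

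The scale carries weight in this trial. Adverse device effects are a stated safety assessment (synopsis and section 5.3), yet section 9.1 does not define the term, so section 9.7 is the only graded basis that the protocol gives for identifying them. Safety is summarised descriptively without tests, so readers will take the causality table at face value. Section 2 says that the study is meant to support a marketing application.

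**Working it through.** No arithmetic applies: the documents give no adverse event rates, and the point concerns the wording of a categorical scale. The check places four kinds of event on the three definitions in section 9.7 and follows each into the rows of section 11.2.6.

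| Kind of event | *Possibly* met? | *Related* met? | Row in 11.2.6 |
|---|---|---|---|
| (a) Device link unlikely but not excluded; another cause could explain it | Yes | No | possibly related |
| (b) Strong timing; another cause unlikely | No | Yes | related |
| (c) Device link plausible; another cause also credible | No: the association is not unlikely | No: the alternative is not unlikely | unknown, if the investigator holds that relatedness cannot be determined |
| (d) Clearly unrelated | No | No | none |

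An example of (c) is an abscess at the target bleeding site a week after bowel surgery, where both the retained material and contamination from the operation are credible causes. Kind (d) is a separate gap and is not part of this point.

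**Order.** By strength of the device link the order is (a), then (c), then (b). The labels given are possibly related, unknown and related. The middle kind leaves the graded rows, and the weakest takes the label that the middle kind should have.

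**Comparison with section 9.1.** Kinds (b) and (c) meet a reasonable-possibility test; kind (a), being unlikely, would not ordinarily do so. As worded, the rows hold:

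- possibly related = (a)
- related = (b)
- unknown = (c), together with events that simply lack information

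The set wanted is (b) and (c). No row, and no combination of rows, gives exactly that set. Adding possibly related to related gives (a) and (b). Adding unknown as well brings in (c), but also keeps (a) and the events that lack information.

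**Where the result is used.**

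1. The causality table in section 11.2.6: affected directly.
2. Identification of adverse device effects: affected, because no other graded basis is stated.
3. Serious events after the follow-up visit: section 9.8.1 makes these reportable only if the investigator judges them related to the device or procedure. An event of kind (c) does not meet the section 9.7 definition of *Related*.
4. Tables by system organ class and preferred term: not affected. They are built whatever the causality score, and kinds (a) to (c) are recorded under section 9.7 as well as under section 9.8.
5. In-study serious events: not affected. Section 9.8.1 requires them to be reported regardless of cause.
6. Efficacy analyses: not affected.

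**The case against.** The strongest reply is that the argument hangs on one word. The rest of the definition of *Possibly* (not excludable, another explanation available) suits an event of kind (c) well, as does the label. Many investigators will score by the label, and nothing in the documents shows that they would misplace such events. This stands as a limit on what can be claimed: how much misclassification would occur is unknown. It does not rescue the text, because an investigator who follows the definition gets the wrong row, and sites may differ in which they follow.

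It can also be said that the section 9.1 wording belongs to the definitions for unanticipated effects and need not be a level of the 9.7 scale. That is right as far as it goes, and the two sections do not contradict each other outright. The difficulty is that the scale offers no way to express the protocol's own test of association.

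Three stronger readings are tempting, and the documents do not support them.

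- A reader might infer that a plausible effect with a competing cause fits no level at all. *Unknown* can take it, although that level is worded for events whose relatedness cannot be determined from the information obtained.
- A reader might infer that a real difference between the products would be hidden. An excess of a given event in one arm would still show by system organ class and preferred term, by arm, whatever its causality score, and in-study serious events are reported regardless of cause. No stated test, endpoint or stopping rule uses the possibly related row.
- A reader might try to put a number on the dilution by pooling possibly related and related events. The rates would have to be invented, section 11.2.6 lists the rows separately and plans no pooled row, and the definitions as written send kind (c) to *Unknown* and not into that pool.

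A neighbouring gap should be kept apart. Section 11.2.6 says that "the worst severity and causality recorded will be used in the by-intensity and by-relationship summaries" but gives no order for *Unknown* against *Possibly*. That would arise with any unknown level and can be settled in the detailed analysis plan promised in section 11.

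**Conclusion.** The point holds. As worded, the scale labels unlikely associations as possibly related and leaves plausible associations with a competing cause to default to *Unknown*, and no level matches the section 9.1 test.

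The consequence is confined to the descriptive causality table, the identification of adverse device effects, and the reporting of serious events after the follow-up visit. It should be corrected, but it does not threaten the primary conclusion or the basic event tables.

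The conclusion assumes that investigators apply the written definitions and not the labels alone, and that adverse device effects are identified from the 9.7 score, since the protocol states no other graded basis.

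**What to change.** In section 9.7, replace the unlikely association in *Possibly* with a reasonable possibility that the device or procedure caused the event, where another cause could also explain it. This aligns the level with section 9.1. Because section 9.8 asks for the relationship to the device and to the surgical procedure as separate items, the definition should be applied to each.

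Put unlikely associations in a level of their own, which section 11.2.6 tabulates but does not count as possibly related. State that events at this level are still recorded: section 9.7 limits the eCRF to attributable events, whereas section 9.8 says that all events, "regardless of their relatedness to the study device or procedure, must be reported in the Adverse Event eCRF". Unless the two are reconciled, a new level could drop events from the basic tables. The order used for worst causality should include the new level.

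The cost is a change of wording and of the eCRF pick-list, with no added visits or subjects, plus re-rating of events already scored. Because the trial is open-label, re-rating by people who know the product could itself bring in bias. Apply it to both arms under the same written rule, and report the scores as first entered alongside the re-rated ones.
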